9.5 Study Size

The study size calculations are based on publicly available annual reports from the Danish and Swedish IVF registers and the previous feasibility study conducted by PPD (34–37). The available data from the IVF registers included the number of initiated stimulation cycles per year and the number of resulting deliveries. The feasibility study report included information on the number of women who had at least one dispensation of a study drug (follitropin alfa or hMG products) per year. Based on the feasibility study report, there will be thousands of women who have dispensed study drugs at least once during the study period, both in Denmark and Sweden.

The study size calculations considered the primary outcome measures, which are LBR, CLBR and MC-CLBR. As stated in Table 7 in Section 9.7.3.3, the denominator for LBR and CLBR is the

number of initiated stimulation cycles with a given study drug and the denominator for MC-CLBR is women who initiated at least one stimulation cycle with a given study drug. To allow for a sufficient time period to detect live births after the initiation of a stimulation cycle, stimulation cycles with the study drugs initiated on or before 31 December 2019 will be considered in the main analysis of the primary objective.

Total amount of data available for the study and the anticipated proportions between study drug use in the study countries

Using the publicly available yearly summary statistics from the Danish and Swedish IVF registers and the number of women with study drug dispensations from the previous feasibility study report, the total amount of available data in the registers was estimated. For the study period, the total number of all initiated stimulation cycles, and the number of women having at least one stimulation cycle with the study drugs and the proportions of study drug used for stimulation cycles were estimated.

The total number of initiated stimulation cycles over the study periods was estimated by summing up all the yearly reported initiated stimulation cycles in the study periods according to the annual reports from the Danish and Swedish IVF registers. For the study period starting from 2010 (HP-hMG comparison), the estimated total number of initiated stimulation cycles (with any drug) is ~100,000 in Denmark and ~115,000 in Sweden. For the study period starting from 2014 (rhFSH-alfa biosimilars comparison), the estimated total number of initiated stimulation cycles (with any drug) is ~58,000 in Denmark and ~65,000 in Sweden.

The proportion of study drug use over the stimulation cycles was estimated by calculating the proportion of women with at least one study drug dispensation from the total number of started stimulation cycles reported yearly. An assumption was made that one woman initiated one stimulation cycle with one study drug per year. In Denmark, the estimated proportion of study drug use was ~53% (study period of 2010-2019) and ~54% (2014-2019) for rhFSH-alfa reference product; ~33% (2010-2019) for HP-hMG; and ~10% (2014-2019) for rhFSH-alfa biosimilar products. In Sweden, the estimated proportion of study drug use was ~36% (2010-2019) and ~35% (2014-2019) for rhFSH-alfa reference product; ~35% (2010-2019) for HP-hMG; and ~28% (2014-2019) for rhFSH-alfa biosimilar products.

Anticipated amount of data available for the study in the study countries

Using the yearly estimated total number of initiated stimulation cycles together with the proportion of study drug use in the study countries, the anticipated number of initiated stimulation cycles available for the study was estimated.

The total number of women who had used each study drug at least once in a stimulation cycle was estimated by summing up the yearly number of women who had dispensed the study drug at least once. It was assumed that the difference in the yearly numbers of women dispensing the study drug and the number of women with a live-birth delivery corresponded to the number of women who continued using the same study drug the next year. The proportion of women delivering per stimulation cycle was estimated per year by calculating the ratio between the number of deliveries and the number of initiated fresh cycles.

The summary of the total anticipated number of initiated stimulation cycles and the number of women per study drug are summarized in Table 2.

Table 2. Anticipated approximate total number of initiated stimulation cycles and women using drug of interest available per study country and study cohorts⁺

	Study period starting 2010		Study period starting 2014	
Country	rhFSH-alfa reference product	HP-hMG products	rhFSH-alfa reference product	rhFSH-alfa biosimilar products
Denmark	53 000 cycles	33 000 cycles	31 000 cycles	5 000 cycles
	19 000 women	12 000 women	14 000 women	3 000 women
Sweden	42 000 cycles	40 000 cycles	22 000 cycles	18 000 cycles
	18 000 women	17 000 women	11 000 women	10 000 women

FSH: follicle-stimulating hormone; hMG: human menopausal gonadotropin; HP: highly purified; rhFSH: recombinant human FSH.

Notes:

⁺ Cycles refer to the approximate number of initiated stimulation cycles with drug of interest on or before 31 December 2019. Women refer to the approximate number of women who are using drug of interest on or before 31 December 2019.

In Sweden, the ratio between the rhFSH-alfa reference product and HP-hMG cycles and users was close to 1:1, which indicates that this study is anticipated to capture similar number of cycles and women for rhFSH-alfa reference product and HP-hMG study cohorts. The ratio between the initiated stimulation cycles with rhFSH-alfa reference product and rhFSH-alfa biosimilar product was ca 1.25 indicating that the rhFSH-alfa reference product study cohort will be approximately 25% larger than the rhFSH-alfa biosimilar product study cohort, in respect to initiated stimulation cycles. Regarding the number of women with rhFSH-alfa reference product and rhFSH-alfa biosimilar product, the study cohorts is anticipated to capture similar number of users.

In Denmark, the ratio between the rhFSH-alfa reference product and HP-hMG users was ca 1.6, which indicates that the rhFSH-alfa reference product study cohort will be approximately 60% larger than the HP-hMG study cohort. The ratio in the number of women between rhFSH-alfa reference product and rhFSH-alfa biosimilar product was as high as 5:1, which indicates that the rhFSH-alfa reference product study cohort is anticipated to include approximately 5 times as many women as the rhFSH-alfa biosimilar product study cohort.

Study size needed to show a conservative minimum detectable difference between the study cohorts

As seen from the estimations above, the number of women having a stimulation cycle with a study drug is the limiting factor for the study size. This is because each woman included in the analysis will have at least one stimulation cycle. Thus, the final study size estimations consider number of women and uses the primary outcome measure of MC-CLBR.

Assuming the above described ratios in the number of women between the study cohorts for the given comparisons, the conservative minimal detectable difference between the study groups was investigated to show the minimal detectable differences in primary outcomes that can be detected in this study. The minimal detectable difference was calculated by using the measure of association in this study: the OR and its corresponding 95% CI. The minimal detectable difference is the difference in the outcome rates between the study cohorts that will yield an OR whose lower 95% CI limit is above 1. In other words, the minimum detectable difference shows the minimal difference between the outcome rates that shows statistically significant difference between the study cohorts. For the conservative estimate, MC-CLBR of 50% in the comparison drug study cohort is used. Table 3 shows the sample size needed for the different conservative estimates of minimum detectable differences between the study cohorts.

Table 3. The study cohort sizes (number of women) needed to show a conservative minimum detectable difference in MC-CLBR (in percentage point (% point)) between the study cohorts⁺

Country	Minimum detectable difference	Study period starting 2010		Study period starting 2014	
		rhFSH-alfa reference product cohort (women)	HP-hMG products cohort (women)	rhFSH-alfa reference product cohort (women)	rhFSH-alfa biosimilar products cohort (women)
Denmark	1.0% point	23 000	14 400	53 000	10 600
	1.5% point	12 000	7 500	27 500	5 500
	2.0% point	6 500	4 100	15 000	3 000
	2.5% point	4 100	2 600	9 500	1 900
	3.0% point	2 800	1 800	6 500	1 300
	4.0% point	1 600	1 000	3 500	700
	5.0% point	1 000	600	2 300	450
Sweden	1.0% point	17 600	17 600	17 600	17 600

		Study period starting 2010		Study period starting 2014	
Country	Minimum detectable difference	rhFSH-alfa reference product cohort (women)	HP-hMG products cohort (women)	rhFSH-alfa reference product cohort (women)	rhFSH-alfa biosimilar products cohort (women)
	1.5% point	8 000	8 000	8 000	8 000
	2.0% point	4 600	4 600	4 600	4 600
	2.5% point	3 000	3 000	3 000	3 000
	3.0% point	2 100	2 100	2 100	2 100
	4.0% point	1 150	1 150	1 150	1 150
	5.0% point	750	750	750	750

HP-hMG: highly purified human menopausal gonadotropin; rhFSH: recombinant human follicle-stimulating hormone; MC-CLBR: multiple-cycle cumulative live birth rate.

Notes:

⁺ Women refer to the approximate number of women who are using drug of interest on or before 31 December 2019

To take into account the effect of the study inclusion and exclusion criteria restricting the study population to a subset of the total population available in the registries, a crude assumption that 75% of the women in the registries are eligible for the study was made. With this crude assumption, the anticipated study size will be able to show any differences of 1.5% point in primary outcomes between the rhFSH-alfa reference product and HP-hMG study cohorts, in both Denmark and Sweden. For the comparison of rhFSH-alfa reference product and biosimilars, the anticipated minimum difference that can be detected in primary outcomes will be 2.5% point in Denmark and 2.0% point in Sweden.

Table 4 shows the minimum detectable difference converted from the percentage point (% point) differences into units of percentage difference between the study cohorts at varying MC-CLBR levels in comparator cohort. Assuming MC-CLBR of 25% or higher in the comparator study cohort, 1.5% point, 2.0% point and 2.5% point differences would correspond to 6.0%, 8.0% and 10.0% or lower percentage differences between the study cohorts. Based on clinical judgment, a difference of 5% between the cohorts is deemed clinically meaningful.

Table 4. The minimum detectable difference converted from percentage point (% point) differences into units of percentage difference between the study cohorts for varying MC-CLBR in the comparator cohort

Minimum detectable difference	MC-CLBR in comparator cohort										
	15%	20%	25%	30%	35%	40%	45%	50%	60%	70%	80%
1.0% point	6.7%	5.0%	4.0%	3.3%	2.9%	2.5%	2.2%	2.0%	1.7%	1.4%	1.3%
1.5% point	10.0%	7.5%	6.0%	5.0%	4.3%	3.8%	3.3%	3.0%	2.5%	2.1%	1.9%
2.0% point	13.3%	10.0%	8.0%	6.7%	5.7%	5.0%	4.4%	4.0%	3.3%	2.9%	2.5%
2.5% point	16.7%	12.5%	10.0%	8.3%	7.1%	6.3%	5.6%	5.0%	4.2%	3.6%	3.1%
3.0% point	20.0%	15.0%	12.0%	10.0%	8.6%	7.5%	6.7%	6.0%	5.0%	4.3%	3.8%
4.0% point	26.7%	20.0%	16.0%	13.3%	11.4%	10.0%	8.9%	8.0%	6.7%	5.7%	5.0%
5.0% point	33.3%	25.0%	20.0%	16.7%	14.3%	12.5%	11.1%	10.0%	8.3%	7.1%	6.3%

MC-CLBR: multiple-cycle cumulative live birth rate.

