Set 4	Stimulation cycles with drug of interest aspirated on or before 30 November 2020 ⁺	Secondary objective 2	Oocytes retrieved per aspirated stimulation cycle
			Embryos cryopreserved per aspirated stimulation cycle
			Utilizable embryos per aspirated stimulation cycle
Set 5	Stimulation cycles with drug of interest initiated on or before 31 August 2020 ⁺	Secondary objective 8	OHSS
Set 6	Fresh and frozen embryo transfers linked to stimulation cycles with drug of interest occurring on or before 31 December 2020 ⁺	Secondary objective 2	Fresh embryos transferred
			Frozen embryos transferred
Set 7	Fresh and frozen embryo transfers linked to stimulation cycles with drug of interest occurring on or before 30 September 2020 ⁺	Secondary objective 3	Implantation rate
Set 8	Women who initiated their first-ever stimulation cycle with drug of interest on or before 31 December 2019	Primary objective	MC-CLBR
		Secondary objective 4	TTLB

CCPR: cumulative clinical pregnancy rate; CLBR: cumulative live birth rate; CPR: clinical pregnancy rate; COPR: cumulative ongoing pregnancy rate; FET: frozen embryo transfer; LBR: live birth rate; MC-CLBR: multiple-cycle cumulative live birth rate; OPR: ongoing pregnancy rate; OHSS: ovarian hyperstimulation syndrome; TTLB: time-to-live birth.

Notes:

*Should data on initiated cycles from the Swedish Q-IVF be available only through 31 December 2019, this analysis set will be adjusted to the same day and month in 2019.

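### The minimum detectable differences in section 9.5 carry no power term: Table 3 is a 50%-power table, and the claimed differences have 58% to 71% power at the anticipated cohort sizes

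*Protocol*

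**What the plan says.** Section 9.5 of the protocol bases study size on women and on MC-CLBR, with a comparator rate of 50%. It counts as detectable a "difference in the outcome rates between the study cohorts that will yield an OR whose lower 95% CI limit is above 1". The section restates this: "the minimum detectable difference shows the minimal difference between the outcome rates that shows statistically significant difference between the study cohorts". No power is given.

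Table 3 lists cohort sizes against differences of 1 to 5 percentage points. Section 9.5 then assumes that 75% of the women counted in Table 2 are eligible and concludes, for HP-hMG in both countries, that "the anticipated study size will be able to show any differences of 1.5% point in primary outcomes". For biosimilars it names 2.5 points in Denmark and 2.0 points in Sweden. The abstract repeats all four figures.

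Section 9.5 also says that "a difference of 5% between the cohorts is deemed clinically meaningful". On whom to count, it says that "the denominator for MC-CLBR is women who initiated at least one stimulation cycle with a given study drug". Table 5 in section 9.7.1 is narrower: MC-CLBR uses Set 8, which is "Women who initiated their first-ever stimulation cycle with drug of interest on or before 31 December 2019".

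**The concern.** The calculation treats the true difference as if it were the observed one. An estimate centred on the value at which the lower limit just reaches 1 falls below that value in about half of repetitions, so a difference chosen this way is detected only about half the time. A reader of the abstract will take a detectable difference to mean one that the study has a good chance of finding.

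What is at stake is how a non-significant country-level result is read. Table 4 equates 2.5 points at a 50% rate with a 5.0% relative difference, which is the size called clinically meaningful. The Danish biosimilar comparison therefore appears to meet that mark exactly.

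**Working it through.** **Inputs (protocol section 9.5).** Comparator rate p0 = 0.50; two-sided 5% (95% CI of the OR). Women from Table 2 at 75%, reference / comparator:

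- Denmark HP-hMG: 0.75 × 19,000 / 12,000 = 14,250 / 9,000
- Sweden HP-hMG: 0.75 × 18,000 / 17,000 = 13,500 / 12,750
- Denmark biosimilar: 0.75 × 14,000 / 3,000 = 10,500 / 2,250
- Sweden biosimilar: 0.75 × 11,000 / 10,000 = 8,250 / 7,500

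**Formulas.** With p1 = p0 + d and cohort sizes n1 (reference) and n0 (comparator):

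- L = ln[p1/(1−p1)] − ln[p0/(1−p0)]
- SE = √[1/(n1·p1) + 1/(n1·(1−p1)) + 1/(n0·p0) + 1/(n0·(1−p0))]
- Lower limit = exp(L − 1.96·SE)
- Power = Φ(L/SE − 1.96)

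**Step 1: reproduce the protocol's figures.** Take the Danish HP-hMG row for 1.5 points (12,000 / 7,500). L = 0.0600, SE = 0.0294, L/SE = 2.04, lower limit 1.002, power Φ(0.08) = 53%. The Swedish row for 1.5 points (8,000 / 8,000) gives L/SE = 1.90, lower limit 0.998, power 47.5%. Over all 21 distinct size pairs, the lower limit is 0.997 to 1.002 and power is 46.7% to 53.1%. The stated sizes are 0.92 to 1.08 times those needed for 50% power, but only 0.45 to 0.53 times those needed for 80%. At the 75%-eligible sizes, the 50%-power differences are 1.32, 1.21, 2.28 and 1.56 points. Rounded up to the Table 3 grid, these are the stated 1.5, 1.5, 2.5 and 2.0.

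**Step 2: power for the claimed differences at the anticipated sizes.** The 80%-power difference solves L/SE = 1.96 + 0.842.

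| Comparison | Claimed (points) | L | SE | L/SE | Power | Miss rate | 80%-power difference (points) |
|---|---|---|---|---|---|---|---|
| Denmark HP-hMG | 1.5 | 0.0600 | 0.0269 | 2.23 | 61% | 39% | 1.89 |
| Sweden HP-hMG | 1.5 | 0.0600 | 0.0247 | 2.43 | 68% | 32% | 1.73 |
| Denmark biosimilar | 2.5 | 0.1001 | 0.0465 | 2.15 | 58% | 42% | 3.25 |
| Sweden biosimilar | 2.0 | 0.0800 | 0.0319 | 2.51 | 71% | 29% | 2.23 |

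Power exceeds 50% here because the anticipated cohorts are larger than the Table 3 row from which each claim is read.

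**Step 3: the 5% difference, read as relative.** At a 50% rate this is 0.05 × 50 = 2.5 points. Power is 96% (Denmark HP-hMG), 98% (Sweden HP-hMG), 88% (Sweden biosimilar) and 58% (Denmark biosimilar). For Danish biosimilars, the 80%-power difference is 3.25/50 = 6.5% relative. That comparison depends on the rate: power for a 5% relative difference is 42% at a 40% rate, 76% at 60% and 92% at 70%.

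**Step 4: loss from weighting (assumption).** The protocol gives no figure. If inverse probability weighting left 80% of the effective sample size, power for the claimed differences would be 51%, 58%, 49% and 61%, and the 80%-power differences would be 2.11, 1.93, 3.63 and 2.50 points.

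**Step 5: whom the counts describe.** The notes to Tables 2 and 3 count women using the drug. Set 8 keeps only women whose first-ever stimulation cycle used it. The 75% factor is attributed to the inclusion and exclusion criteria, which do not require a first-ever cycle. The true denominator is therefore smaller than the one used. The protocol gives no figure from which to size the gap.

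**The case against.** The definition is disclosed, no power is claimed anywhere in section 9.5, and the stated figures follow from that definition. This stands: a reader might infer a calculation error, and there is none. The fault lies in calling the result detectable and in the capability claim built on it.

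A reader might also infer that the study has only about 50% power for its claimed differences and would miss them up to half the time. The documents do not support that. About 50% describes the Table 3 sizes. At the anticipated sizes the miss rate is 29% to 42%, and it reaches half only under an assumed weighting loss.

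Nor is the study generally too small for a clinically meaningful effect. At a 50% rate, three of the four comparisons have 88% to 98% power for a 5% relative difference.

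Other mitigations are real but partial:

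- **Cycle-based outcomes.** LBR and CLBR use cycles, which are more numerous. At 75% of the Table 2 cycles and a 50% rate, power for the claimed differences is 81% to 96%. This is an upper bound, because it ignores repeated cycles within a woman and weighting. The protocol's claim was calculated on MC-CLBR.
- **Pooling.** A fixed-effect combination of the two countries would give about 91% power for HP-hMG at 1.5 points and 97% for biosimilars at 2.5 points. Section 9.7.3.8 only says that meta-analysis will be considered, and the claim is made country by country.
- **Fixed cohort.** The register population is what it is, and results come with 95% CIs, so a careful reader can judge a null result from its interval. This limits the harm but does not make the stated capability correct.

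**Conclusion.** The concern holds in this form. The detectable differences in section 9.5 and the abstract are significance thresholds. Table 3 carries 47% to 53% power. At the protocol's own eligible sizes and a 50% comparator rate, the claimed differences have 61%, 68%, 58% and 71% power, and none reaches 80%. The statement that the study will be able to show any difference of that size is not supported.

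These results rest on the protocol's counts, its 75% eligibility factor and the 50% rate, with no loss from weighting. Both that loss and the restriction to first-ever starters would lower power. A lower comparator rate raises power for a fixed point difference: at an assumed 25% it is 68% to 82%, and only Swedish biosimilars pass 80%. The same change lowers power for a fixed relative difference.

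The comparison most affected is Danish biosimilars, where the claim coincides with the 5% mark but has about 58% power.

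**What to change.** In section 9.5 and the matching abstract paragraph:

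1. State a power, for example 80%, and recompute Table 3 for it. Otherwise label Table 3, and only Table 3, as giving about 50% power. That label would be wrong for the four conclusions drawn from the anticipated sizes.
2. Restate those conclusions at 80% power before weighting loss: about 1.9 points (Denmark HP-hMG), 1.7 (Sweden HP-hMG), 3.3 (Denmark biosimilar) and 2.2 (Sweden biosimilar). An illustrative row at 80% effective sample size, marked as an assumption, would read 2.1, 1.9, 3.6 and 2.5.
3. Delete the claim to show any difference of the stated size.
4. Say that for a 5% relative difference at a 50% rate the HP-hMG comparisons and the Swedish biosimilar comparison have 88% to 98% power before weighting loss, and the Danish biosimilar comparison about 58%.
5. Re-base the counts on first-ever starters, as Set 8 requires, if such counts can be obtained. The sources listed in section 9.5 report cycles, deliveries and women with a dispensation, so they may not supply them. In that case, state that the figures are optimistic for this reason.

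Items 1 to 4 are text and table changes that need no further data and no change to the analysis. Their cost is that the stated figures become less favourable. Item 5 may need a further count from the registers or, failing that, one sentence of caveat.

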
Study Size
	
The study size was estimated for the primary outcome of live birth (measured as LBR, CLBR and MC-CLBR) based on publicly available annual reports from the Danish and Swedish IVF registers and the previous feasibility study conducted by PPD .
 
As each woman to be included in the analysis will have at least one stimulation cycle, the number of women having a stimulation cycle with a study drug is the limiting factor for the study size. Thus, the study size was estimated based on the number of women and using the outcome measure of MC-CLBR.
 
The anticipated approximate maximum number of women who have initiated a stimulation cycle with a study drug, and will be available for the comparison of rhFSH-alpha reference product and HP-hMG products (study period starting in 2010), is as follows:
 
 • 19,000 women in rhFSH-alpha reference product cohort and 12,000 women in HP-hMG cohort, in Denmark • 18,000 women in rhFSH-alpha reference product cohort and 17,000 women in HP-hMG cohort, in Sweden 
For the comparison of rhFSH-alfa reference product and rhFHS-alfa biosimilar products (study period starting in 2014), the corresponding numbers are the following:
 
 • 14,000 women in rhFSH-alpha reference product cohort and 3,000 women in rhFSH-alpha biosimilar product cohort, in Denmark • 11,000 women in rhFSH-alpha reference product cohort and 10,000 women in rhFSH-alpha biosimilar product cohort, in Sweden 
The conservative minimal detectable difference between the study groups was investigated to show the minimal differences in primary outcomes that can be detected in this study. The minimal detectable difference was calculated by using the measure of association in this study: odds ratio (OR) and its corresponding 95% confidence interval (CI). The minimal detectable difference is the difference in the outcome rates between the study cohorts that will yield an OR whose lower 95% CI is above 1.
 
To take into account the effect the study inclusion and exclusion criteria, a crude assumption that 75% of the women are eligible for the study. With this assumption, the anticipated study size will be able to show any differences of 1.5 percentage point (% point) in primary outcomes between the rhFSH-alfa reference product and HP-hMG study cohorts, in both Denmark and Sweden. For comparison of rhFSH-alfa reference

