9.7.3.3 Rates and Numbers

The results of the study outcomes in the study cohorts will be estimated by calculating the outcome measures according to their definitions (see Table 7) in both original and IPTW-weighted study cohorts.

For the analyses of LBR, a woman may contribute up to one delivery resulting in live birth. For the analyses of CLBR, a woman may contribute several deliveries resulting in live birth per each stimulation cycle. The same principle applies to the analyses of clinical and ongoing pregnancies, *i.e.*, a woman may contribute several clinical and ongoing pregnancies for the analyses of CCPR and COPR, respectively.

For the analysis of MC-CLBR, where the woman is the unit of analysis, only the first occurrence of a live birth per woman within the first five stimulation cycles using the same study drug will be considered. The MC-CLBR analysis will be performed by cycle rank, *i.e.*, analyzed as the cumulative probability of a live birth up to and including the first, second, third, fourth and fifth stimulation cycle, respectively. The MC-CLBR analysis will be restricted to women who initiated their first-ever stimulation cycle during the study period.

In the assessment of MC-CLBR, it is assumed that women who did not return during the study period for another stimulation cycle after a failed attempt (*i.e.*, who did not have a live birth), did not have any live birth. Thus, for the main analysis, the MC-CLBRs will be calculated as conservative estimates (20). Optimal estimates will be provided in a sensitivity analysis restricted to the primary objective (see Analysis 2 Section 9.7.3.9).

Rates and numbers will be expressed as the rate or number per 100 units of observations with 95% CI.

Table 7. Definitions of outcome measures

Study objective	Outcome measure	Numerator	Denominator
Primary objective	LBR	Number of deliveries with at least one live birth after fresh embryo transfer	Initiated cycles with drug of interest
	CLBR	Number of deliveries with at least one live birth after one initiated stimulation cycle, including all fresh or frozen embryo transfers linked to that cycle	Initiated cycles with drug of interest
	MC-CLBR	Number of deliveries with at least one live birth after each initiated stimulation cycle in up to five cycles, including all fresh or frozen embryo transfers linked to each of those stimulation cycles	Women who initiated 1, 2, 3, 4 or 5 cycles with drug of interest

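### The Danish detectable differences for MC-CLBR are computed on all users of a study drug, not on the first-ever-cycle women in whom MC-CLBR is analysed, so they are not supported for that population

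*Protocol*

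**What the plan says.** - **Basis of the count.** Section 9.5: "The total number of women who had used each study drug at least once in a stimulation cycle was estimated by summing up" the yearly numbers of women dispensing it. To avoid counting a woman twice, the yearly dispensing women who did not deliver are taken to have "corresponded to the number of women who continued using the same study drug the next year". The note to Table 2 confirms the basis: "Women refer to the approximate number of women who are using drug of interest on or before 31 December 2019". Section 9.5 also describes the MC-CLBR denominator as women with at least one cycle on the drug.
- **Totals for Denmark** (abstract, Study Size): "19,000 women in rhFSH-alpha reference product cohort and 12,000 women in HP-hMG cohort, in Denmark" for the comparison from 2010, and "14,000 women in rhFSH-alpha reference product cohort and 3,000 women in rhFSH-alpha biosimilar product cohort, in Denmark" for the comparison from 2014.
- **Reduction.** "a crude assumption that 75% of the women in the registries are eligible for the study was made". The sentence ties this to the inclusion and exclusion criteria.
- **Claims.** Section 9.5 and the abstract then state detectable differences of 1.5 points against HP-hMG in both countries, and of 2.5 points (Denmark) and 2.0 points (Sweden) against biosimilars.
- **Analysis population.** Section 9.7.1, Table 5, Set 8 (MC-CLBR and time to live birth): "Women who initiated their first-ever stimulation cycle with drug of interest on or before 31 December 2019". Section 9.7.3.3: "The MC-CLBR analysis will be restricted to women who initiated their first-ever stimulation cycle during the study period".

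**The concern.** The population sized is wider than the population analysed. The exclusion criteria in Section 9.2.1 remove a cycle only after five or more earlier ones, so women with up to four previous cycles are eligible. The same section says that outcome-specific selection is applied in addition. The first-ever restriction is therefore not part of what the 75% stands for.

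Two groups counted in Table 2 fall outside Set 8:

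1. Women already in treatment when the study period opens.
2. Women who reach the drug after a first cycle on another product. Section 9.2.2 lets one woman contribute to several cohorts, but she has only one first-ever cycle. This group is likely to matter most for the biosimilars, whose comparison starts at reimbursement in 2014 and whose use grew gradually (Section 9.9.2).

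At stake is how a null Danish result would be read. Section 9.5 calls a 5% relative difference clinically meaningful. At the assumed 50% comparator rate, Table 4 equates 2.5 points with exactly 5.0%, so any loss beyond the margin moves the Danish biosimilar comparison past that mark.

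**Working it through.** **Inputs.** Women from Table 2; eligible share 75%; required sizes from Table 3; comparator rate 50%; criterion that the lower 95% limit of the odds ratio lies above 1 (all Section 9.5). The first-ever share s of eligible women is not in the protocol and is treated as an assumption.

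**Step 1: reproduce the plan's read-off** (Table 2 × 0.75, reference/comparator).

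| Comparison | Eligible women | Table 3 requirement | Claim |
|---|---|---|---|
| Denmark, HP-hMG | 14,250 / 9,000 | 12,000 / 7,500 | 1.5 points |
| Denmark, biosimilar | 10,500 / 2,250 | 9,500 / 1,900 | 2.5 points |
| Sweden, HP-hMG | 13,500 / 12,750 | 8,000 / 8,000 | 1.5 points |
| Sweden, biosimilar | 8,250 / 7,500 | 4,600 / 4,600 | 2.0 points |

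All four claims follow from the table when s = 100%.

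**Step 2: break-even share against Table 3** (requirement ÷ eligible).

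- Denmark, HP-hMG: 12,000/14,250 = 84%; 7,500/9,000 = 83%.
- Denmark, biosimilar: 9,500/10,500 = 90%; 1,900/2,250 = 84%.
- Sweden, HP-hMG: 8,000/13,500 = 59%; 8,000/12,750 = 63%.
- Sweden, biosimilar: 4,600/8,250 = 56%; 4,600/7,500 = 61%.

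**Step 3: direct solution.** With p0 = 0.50 and p1 = 0.50 + d, solve ln[p1/(1−p1)] − ln[p0/(1−p0)] = 1.96 × SE, where SE = √[1/(n1·p1(1−p1)) + 1/(n0·p0(1−p0))]. Table 3 is only roughly reproduced. For Denmark the formula needs 11,095/6,934 where Table 3 has 12,000/7,500 (about 8% fewer), and 9,208/1,842 where it has 9,500/1,900 (about 3% fewer). Both yardsticks are therefore shown.

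Detectable difference in points, with eligible women multiplied by a common s:

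| s | 100% | 90% | 80% | 70% | 60% | 50% |
|---|---|---|---|---|---|---|
| Denmark, HP-hMG (claim 1.5) | 1.32 | 1.39 | 1.48 | 1.58 | 1.70 | 1.87 |
| Denmark, biosimilar (claim 2.5) | 2.28 | 2.40 | 2.54 | 2.72 | 2.94 | 3.22 |
| Sweden, HP-hMG (claim 1.5) | 1.21 | 1.28 | 1.35 | 1.45 | 1.56 | 1.71 |
| Sweden, biosimilar (claim 2.0) | 1.56 | 1.65 | 1.75 | 1.87 | 2.02 | 2.21 |

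Break-even s by this route: 77%, 83%, 65% and 61%.

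**Step 4: how large might the loss be?** This is an illustration only. It assumes constant yearly use and reads Table 2 as one year's users plus yearly new users. For the Danish reference cohort from 2010, yearly users are 53,000/10 = 5,300 and new users are (19,000 − 5,300)/9 = 1,522 a year. Over ten years that gives 15,222 women new to the drug, or 80% of 19,000. The same steps give 9,667 of 12,000 (81%) for Danish HP-hMG and 10,600 of 14,000 (76%) for the Danish reference cohort from 2014. After the 75%, the HP-hMG comparison has 11,417/7,250 women. That is short of Table 3's 12,000/7,500, but by direct solution the detectable difference is 1.47 points, inside the claim. Women who switched from another drug are not yet removed.

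**The case against.** The strongest reply is that the correction can run in both directions. Table 2 assumes that every woman without a delivery continues on the same drug. Women who stop and are replaced by new patients are therefore missed, and Section 9.1.1 itself says that the number continuing falls substantially with each cycle. In the illustration above, suppose 10% of the continuing women stop each year and are replaced (an assumption). The Danish reference cohort then has 10 × (1,522 + 0.10 × 3,778) = 19,000 women new to the drug, where 3,778 = 5,300 − 1,522. That is exactly the Table 2 figure. This stands: the offset is real and its size is unknown.

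It also stands that the steady-state figures are solved from Table 2 and do not test it, that removing first-year patients alone leaves Danish HP-hMG at 1.47 points, and that the protocol calls its 75% crude and presents the counts as approximate maxima. The study takes all eligible register cycles, so no recruitment decision depends on Section 9.5. The per-cycle outcomes LBR and CLBR rest on larger counts.

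A reader might infer that the 1.5-point and 2.5-point claims are false, or that the first-ever restriction demonstrably uses up the Danish margin. The documents do not support that, because the deciding quantity, the first-ever share, appears nowhere in them. What the reply does not remove is that Section 9.5 names MC-CLBR as its sizing outcome and makes no allowance for the set in which MC-CLBR is analysed.

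**Conclusion.** The mismatch between the sizing population and Set 8 is explicit in the protocol. The Danish claims are unsupported for the women who will be analysed. They hold only if the first-ever share of eligible women is at least about 84% (HP-hMG) or 84% to 90% (biosimilars) against Table 3, or about 77% and 83% by direct solution with the same share in both cohorts. The Swedish claims hold down to a share of about 56% to 65%, depending on comparison and yardstick, and are not in question on any moderate assumption.

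These break-evens rest on the protocol's 75%, its 50% comparator rate and its own definition of detectability, which corresponds to roughly 50% power at the detectable difference. The conclusion is that the figures need restating, not that the study cannot meet them.

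**What to change.** In Section 9.5 and the abstract:

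1. Change the MC-CLBR denominator in Section 9.5 to match Set 8.
2. Apply a stated first-ever share on top of the 75%, separately by drug if the feasibility data allow it.
3. Replace the single Danish claims by a range labelled as assumption-based. On the protocol's definition, a common share of 100% to 50% gives about 1.3 to 1.9 points for HP-hMG and about 2.3 to 3.2 points for biosimilars.
4. State that the continuation assumption behind Table 2 may undercount new women and partly offset the loss.

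The cost is a recalculation, some rewording and somewhat less favourable stated figures. Enrolment, design and analysis do not change.
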